8.2 Sample size determination

Based on the placebo and effect responses for adalimumab in the PIONEER trials (Kimball, 2016) for moderate-to-severe HS, the HiSCR response rate in the placebo group was approximately 27% (26.0% and 27.6%) and HiSCR rates of 42-59% for adalimumab. In mild-to-moderate and moderate-only HS treated with apremilast, the placebo HiSCR rate was 0% and in the response rate in the intervention groups was 53-55% (Kerdel 2019, Vossen 2019).

With a sample size of at least 18 participants, we will have sufficient power to determine if the HiSCR response rate for topical ruxolitinib 1.5% cream is 55% and significantly different from a 20% (or lower) placebo response rate with a power of 80% and risk of type I error of 5%. Typically, in a Simon's two-stage design, 11 patients would be accrued in the first stage and 7 additional in the second phase; however, we will accrue all in one cohort of at least 18 completed participants. The null hypothesis will be rejected if 5 or more responses are observed in 18 completed participants.

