8.0 Subject Numbers and Statistical Plan

8.1 Number of Subjects

We aim to enroll at least 18 subjects to complete the interventional study to assess the primary endpoint. Anticipating screen failures and loss-to-follow-up we anticipate screening and enrolling approximately 24 people with hidradenitis suppurativa. No additional participants with *any* biologic use will be enrolled after 30% of participants with stable dosage and frequency of a biologic are enrolled.

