8.3 Statistical methods

The PI cannot be involved in the primary data analysis, but can maintain involvement in the data interpretation required for authorship. The primary statistical analysis to evaluate the null hypothesis that the proportion of participants that achieve HiSCR at Week 16. P-values ≤ 0.05 will be considered significant. The primary efficacy analysis will be carried out in the ITT Population, defined as all patients who complete the study. Last-observation-carried-forward will be used for missing data.

Secondary endpoints include the mean change in the AN count at Week 16; mean change in DLQI score from Baseline to Week 16; mean change in the novel clinician-reported outcome measure (HASI, investigator-supplied) score from Baseline to Week 16; mean change in novel HS patient-reported outcome measure (HiSQOL, Investigator-supplied) from Baseline to Week 16. Secondary efficacy variables will be summarized in the ITT Population. Statistical tests from laboratory assays will be done with the assistance of Penn State biostatisticians. Analyses can include paired t-tests, repeated measure ANOVA and regression-based analyses depending on the number of replicates, samples and repeated measures captured during each assay.

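### Declaring success at 5 or more responders of 18 carries a 28% false-positive rate against the 20% null, not the stated 5%, and fits a 10% versus 35% design

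*Combined protocol and SAP*

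**What the plan says.** Section 8.2 (Sample size determination) plans a single-arm comparison with a fixed reference rate. The target is that "the HiSCR response rate for topical ruxolitinib 1.5% cream is 55" per cent, to be shown "significantly different from a 20% (or lower) placebo response rate with a power of 80% and risk of type I error of 5" per cent. The section mentions a Simon two-stage layout in which "11 patients would be accrued in the first stage and 7 additional in the second phase", but sets it aside: "however, we will accrue all in one cohort of at least 18 completed participants". The decision rule is: "The null hypothesis will be rejected if 5 or more responses are observed in 18 completed participants".

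Section 8.3 (Statistical methods) gives a second criterion for the same endpoint, "P-values ≤ 0.05 will be considered significant", without naming the test, its sidedness or the reference rate. Section 8.1 (Number of Subjects) sets 18 completers as a minimum, "We aim to enroll at least 18 subjects to complete the interventional study to assess the primary endpoint", and expects to screen and enrol about 24.

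**The concern.** Five of 18 is 27.8%, only one to two responders above what a 20% rate would give on average (18 × 0.20 = 3.6). A cut-off that close to the null expectation cannot hold type I error at 5% with 18 patients. It is also almost the same as the higher of the two placebo HiSCR rates that Section 8.2 cites from the adalimumab trials (26.0% and 27.6%).

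The trial has no control arm and no blinding, so this threshold is its only formal protection against reading a placebo-level response as efficacy. If the Section 8.2 rule decides, a cream with a true response rate of 20% would be declared effective more than one time in four. If Section 8.3 decides, the same data could be non-significant. The primary conclusion would depend on which section the analyst follows.

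**Working it through.** **Inputs, all from Section 8.2:** n = 18 completers; null rate p0 = 20% or lower; alternative p1 = 55%; type I error 5%; power 80%; reject at 5 or more responders. Error must be controlled across the whole null, so it is evaluated at its upper end, 20%.

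**Formula.** With X ~ Binomial(n, p), P(X ≥ k) = 1 − Σ C(n, x) pˣ (1 − p)ⁿ⁻ˣ, summed over x = 0 to k − 1.

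**1. The plan's own rule.** At p = 0.20 and n = 18, the probabilities of 0, 1, 2, 3 and 4 responders are 0.0180, 0.0811, 0.1723, 0.2297 and 0.2153, summing to 0.7164. Hence P(X ≥ 5) = 1 − 0.7164 = **0.2836**, against a stated 0.05. At p = 0.55, P(X ≥ 5) = **0.9951**, against a stated 0.80. Neither stated figure is reproduced.

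**2. Other cut-offs at n = 18**

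| Reject at | Type I error at 20% | Power at 55% |
|---|---|---|
| ≥ 5 | 0.2836 | 0.995 |
| ≥ 6 | 0.1329 | 0.982 |
| ≥ 7 | 0.0513 | 0.946 |
| ≥ 8 | 0.0163 | 0.872 |

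The smallest cut-off with exact error at or below 5% is 8; a cut-off of 7 just misses.

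**3. Conflict with Section 8.3.** The type I error column is also the exact one-sided p-value for observing exactly that many responders. So 5, 6 or 7 of 18 (p = 0.284, 0.133, 0.0513) succeeds under Section 8.2 and is non-significant under Section 8.3 with an exact test. The exact 95% confidence interval for 5/18 is 9.7% to 53.5%, which includes 20%.

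**4. Would the two-stage layout rescue it?** The probability of rejecting at ≥ 5 of 18, at a true 20%, after a futility stop at 11 patients:

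| Stop if responders of 11 are | Type I error at 20% |
|---|---|
| 0 | 0.283 |
| ≤ 1 | 0.275 |
| ≤ 2 | 0.232 |
| ≤ 3 | 0.138 |
| ≤ 4 | 0.0504 |

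Only the most severe stop comes near 5%, and the plan uses no stage at all.

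**5. What design do 11, 7, 18 and 5 fit?** A search over Simon designs (error ≤ 0.05, power ≥ 0.80) for 10% versus 35% gives this minimax design: 11 patients, stop at ≤ 1 responder, 18 in total, reject at ≥ 5 (error 0.027, power 0.8005). The smallest exact single-stage design for those rates is also 18 with ≥ 5 (error 0.028, power 0.811). For 20% versus 55%, the minimax total is 11, the optimal total is 14, and the smallest single-stage design is 13 with ≥ 6 (error 0.030, power 0.821).

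**6. More than 18 completers.** Smallest cut-off with exact one-sided error ≤ 5% at p0 = 20%:

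| n | Cut-off | Type I error | Power at 55% |
|---|---|---|---|
| 18 | 8 | 0.016 | 0.872 |
| 19 | 8 | 0.023 | 0.913 |
| 20 | 8 | 0.032 | 0.942 |
| 21 | 8 | 0.043 | 0.962 |
| 22 | 9 | 0.020 | 0.938 |
| 23 | 9 | 0.027 | 0.959 |
| 24 | 9 | 0.036 | 0.973 |

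If all 24 completed and the cut-off stayed at 5, P(X ≥ 5) at 20% would be 0.540.

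**The case against.** **The null allows rates below 20%.** The rule's error is 12.1% at a true 15% and 2.8% at 10%. But a test of 20% or lower must hold its error at 20%, and no 10% null is set anywhere. This does not help the rule.

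**Sidedness is not stated.** That is true, and it affects part of the remedy. A rule that rejects only for many responders, against a null of 20% or lower, reads naturally as one-sided 5%. If 2.5% per side were intended, the cut-offs for n = 20, 21, 23 and 24 would each rise by one. The cut-off of 8 at n = 18 stands either way (0.0163), and no convention turns 28% into 5%.

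**Section 8.3 might govern.** An exact test at p ≤ 0.05 would keep one-sided error within 5%. The precise charge is therefore two conflicting criteria, one of them with 28% error. The plan does not say which prevails.

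**The error may lie in the rates.** This is a fair point. A cut-off of 5 of 18 is coherent for 10% versus 35%, so restating and justifying those rates would also remove the contradiction. That the numbers came from such a design is an inference from the match; the 28.4% does not depend on it.

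**Two comparisons need care.** The 54% figure is an extreme, because the 24 allows for screen failures and loss to follow-up. The 26.0% and 27.6% placebo rates come from moderate-to-severe disease, whereas this trial enrols Hurley stage I and II, and the section also cites a 0% placebo rate in milder disease.

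**Conclusion.** The concern holds and must be fixed. Against the stated 20% null, rejecting at 5 or more of 18 has an exact type I error of 28.4%, more than five times the stated 5%, and power of 99.5% at 55% instead of 80%. The rule contradicts the error rate in its own section and the significance level in Section 8.3, and it is undefined above 18 completers. The result assumes only independent binary responses, a single analysis as planned, and the 20% null as written. The replacement cut-offs further assume one-sided 5%.

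**What to change.** In Section 8.2, replace the rule with an exact binomial test against 20%, state that it is one-sided at 5%, and give a cut-off for every possible number of completers: at least 8 responders for n = 18 to 21, and at least 9 for n = 22 to 24. Report the exact operating characteristics, which at n = 18 are type I error 1.6% and power 87% at a true 55%. Delete the two-stage sentence, or give the stage bounds if stages are to be used. In Section 8.3, name the same test, reference rate and sidedness, so that one criterion decides the primary endpoint.

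If the sponsor instead means to keep 5 of 18, the null and target rates must be restated and justified to fit it, and cut-offs above 18 are still needed.

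The text change is short, but it alters the primary decision rule, so it should be made as a dated amendment before the primary outcome data are examined. No more patients are needed for 80% power at 55%. The cost is a stricter bar: at a true rate of 50%, at least 8 of 18 has 76% power.

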8.3 Statistical methods

The PI cannot be involved in the primary data analysis, but can maintain involvement in the data interpretation required for authorship. The primary statistical analysis to evaluate the null hypothesis that the proportion of participants that achieve HiSCR at Week 16. P-values ≤ 0.05 will be considered significant. The primary efficacy analysis will be carried out in the ITT Population, defined as all patients who complete the study. Last-observation-carried-forward will be used for missing data.

Secondary endpoints include the mean change in the AN count at Week 16; mean change in DLQI score from Baseline to Week 16; mean change in the novel clinician-reported outcome measure (HASI, investigator-supplied) score from Baseline to Week 16; mean change in novel HS patient-reported outcome measure (HiSQOL, Investigator-supplied) from Baseline to Week 16. Secondary efficacy variables will be summarized in the ITT Population. Statistical tests from laboratory assays will be done with the assistance of Penn State biostatisticians. Analyses can include paired t-tests, repeated measure ANOVA and regression-based analyses depending on the number of replicates, samples and repeated measures captured during each assay.

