1.2 Primary Study Endpoints

The primary efficacy measure is the proportion of participants that achieve HiSCR (is the total number of abscess and inflammatory count of the participants lesions) at Week 16 with topical ruxolitinib 1.5% cream as compared to Baseline (Week 0). The HiSCR is defined as at least a 50% reduction in the total abscess and inflammatory nodule count (AN count) for all study body sites with no increase in abscess count and no increase in draining fistula count relative to Baseline. The primary efficacy analysis will be carried out on all participants who complete 16 weeks of treatment.

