3.3 Early Withdrawal of Subjects

3.3.1 Criteria for removal from study

Some possible reasons for an early withdraw might be subjects require or receive treatment that is not allowed in this study, subject becomes pregnant, subject experiences side effects from the study treatments that they find unacceptable, HS worsens according to the study doctor's assessment, or subject does not follow instructions.

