3.3.2 Follow-up for withdrawn subjects

If a subject withdraws completely from the research study, no further information will be collected and his/her participation will end. All attempts will be made to conduct the last study visit and perform all early termination assessments.

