In the event of an acutely painful lesion that requires immediate intervention, the investigator and participant will have the option to perform protocol-allowed interventions. Two types of interventions are permitted: injection with intralesional triamcinolone acetonide suspension (up to 40 mg in total at the same visit) and/or incision and drainage. New systemic and topical therapies following incision and drainage, including antibiotics, are prohibited. Participants should continue using the topical study therapy. From Day 1 through Week 16, an intervention can occur on a maximum of 2 different lesions at the same visit or on the same lesion at 2 different study visits. The same lesion cannot be treated 2 times during the same visit. If participants require more than 3 interventions before Week 16, then the study drug will be discontinued for those participants. Study procedures must be performed before any interventions. Any lesion undergoing an intervention will be documented in the lesion count worksheet.

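### The primary set is labelled ITT but consists of completers, is defined in two different ways, and probably biases the HiSCR rate upward

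*Combined protocol and SAP*

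**What the plan says.** Three statements govern the primary denominator.

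- Section 8.3: "The primary efficacy analysis will be carried out in the ITT Population, defined as all patients who complete the study".
- Section 1.2: "The primary efficacy analysis will be carried out on all participants who complete 16 weeks of treatment".
- Section 8.2 sizes the trial and states its decision rule on completers: "we will accrue all in one cohort of at least 18 completed participants".

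On missing data, 8.3 adds: "Last-observation-carried-forward will be used for missing data". The plan contains no non-responder rule, no analysis of all treated participants and no sensitivity analysis. Secondary efficacy variables are summarised in the same set.

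Participants can leave the trial or stop the drug by several routes:

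- Section 3.3.1 gives possible withdrawal reasons. They include "HS worsens according to the study doctor's assessment", treatment not allowed in the study, unacceptable side effects, pregnancy and not following instructions.
- Section 7.4.6.5: "If participants require more than 3 interventions before Week 16, then the study drug will be discontinued for those participants".
- The action table in 18.2 takes participants off the drug for possibly related adverse events, down to Grade 1 or 2.

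For those who withdraw, 3.3.2 says: "All attempts will be made to conduct the last study visit and perform all early termination assessments". Section 7.2.5 makes this a combined Week 16/early termination visit with clinician-reported measures.

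**The concern.** A set of completers is not an intention-to-treat set. Here the label matters because some exits are themselves signs that treatment failed: worsening disease, need for a prohibited therapy, repeated rescue. Removing those people from the denominator raises the observed response rate. The trial has one arm and is tested against a fixed 20%, so no control group is subject to the same selection.

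The definitions also disagree. Someone taken off the drug after repeated rescue who still attends Week 16 has not completed 16 weeks of treatment (1.2) but may have completed the study (8.3). LOCF adds a third reading: it has a real job only if non-completers are analysed, which both definitions rule out. In an open-label trial, this choice should not remain open until the data are seen.

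**Working it through.** **Inputs.** Null rate 20%, target 55%, type I error 5%, power 80%, at least 18 completers, rejection at 5 or more responses (8.2). About 24 people screened and enrolled, allowing for screen failures and loss to follow-up (8.1). The split between the two is not given, so treated non-completers are taken as 0 to 6.

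**The plan's own figure.** For X ~ Binomial(18, p):

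- P(X ≥ 5 | 0.20) = 28.4% and P(X ≥ 5 | 0.55) = 99.5%. The stated 5% and 80% are not reproduced. That is a separate defect.
- P(X ≥ 7 | 0.20) = 5.13%.
- P(X ≥ 8 | 0.20) = 1.6% and P(X ≥ 8 | 0.55) = 87.2%.

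I use 8 of 18, the smallest cut-off with type I error below 5%, so that the effect of the population is not mixed with that of the low threshold. The written rule is shown alongside.

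**Size of the inflation.** Let N be the number treated, with 18 completing and all N − 18 others non-responders. If the all-treated rate is p, the completer rate is p × N/18. The factor is 20/18 = 1.11, 22/18 = 1.22 or 24/18 = 1.33.

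**Type I error when the all-treated rate is 20%:**

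| Treated | Completer rate | P(≥8 of 18) | P(≥5 of 18) |
|---|---|---|---|
| 18 | 20.0% | 1.6% | 28.4% |
| 20 | 22.2% | 3.0% | 37.0% |
| 22 | 24.4% | 5.1% | 45.9% |
| 24 | 26.7% | 8.0% | 54.7% |

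**Relaxing the assumption on dropouts.** With 24 treated and the six dropouts responding at 10%, the completer rate is (0.20 × 24 − 0.10 × 6)/18 = 4.2/18 = 23.3%, and P(≥8 of 18) = 3.9%.

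**Same data, two denominators.** Eight responders give 8/18 = 44.4%, one-sided exact p = 0.016. With six non-responding dropouts added, 8/24 = 33.3%, p = 0.089.

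**All-treated rule.** Exact cut-offs against 20%:

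- 20 treated: P(X ≥ 8) = 3.2%.
- 24 treated: P(X ≥ 9) = 3.6%.

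Power at 9 of 24, with 55% response among completers and dropouts counted as failures:

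- No dropout: rate 0.55, power 97%.
- 15% dropout: 0.55 × 0.85 = 0.4675, power 87%.
- 25% dropout: 0.55 × 0.75 = 0.4125, power 72%. If exactly 18 complete, P(X ≥ 9 | 18, 0.55) = 75%.

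**The case against.** Much of the case on the other side concerns size and certainty, and most of it stands.

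- **The 24.** A reader might infer that the plan expects six treated people to drop out. It does not: the 24 includes screen failures, who never receive the drug. Six is a ceiling.
- **The 8.0%.** It combines that ceiling with non-response in every dropout. At 8 of 18 the error passes 5% only near this extreme. The rise from 28% to 55% starts from the separate fault in the 5-of-18 rule.
- **Direction.** It is tempting to say the bias can only favour efficacy. Pregnancy, non-compliance, loss to follow-up and mild adverse events can also remove responders. Upward bias is likely, not certain.
- **Rescue.** A reader might infer that heavy rescue always removes a participant from the analysis. Section 7.4.6.5 stops the drug, not participation. Exclusion is clear only under 1.2.
- **LOCF.** A reader might infer that LOCF would routinely turn a Week 4 or 8 response into a Week 16 success. Because an early termination assessment is attempted, the last observation in someone leaving for worsening would usually be that visit, and would carry failure forward. An early response is carried forward only if that visit is missed.
- **Remedy.** Counting dropouts as non-responders also penalises people lost for unrelated reasons, and it is not the only defensible choice.

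None of this reconciles 1.2 with 8.3, justifies the ITT label, or supplies the missing all-treated analysis.

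**Conclusion.** The point holds and needs correcting before analysis. The primary set is mislabelled, defined in two incompatible ways, and paired with a missing-data rule that hardly applies to it. The completer rate is probably biased upward because several exits reflect treatment failure. The size is unknown. If all dropouts fail, the inflation factor is N/18, at most 1.33 if 24 is taken as the most who could be treated and 18 complete. On the same assumption, type I error at 8 of 18 reaches at most 3.0%, 5.1% or 8.0% with 20, 22 or 24 treated, against 1.6% without dropout. It is 3.9% if six dropouts respond at 10%. The documents do not support a claim that efficacy would certainly be overstated, or that six treated dropouts are expected.

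**What to change.** In 1.2, 8.2 and 8.3:

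1. Define one primary set: all participants who apply study drug at least once. Drop the ITT label for completers.
2. Count as a non-responder anyone without a valid Week 16 HiSCR, or who stopped the drug for worsening, prohibited therapy or excess rescue.
3. Remove LOCF for the primary endpoint.
4. Keep the completer analysis as supportive, with a single definition of completion.
5. Fix the exact cut-off by the number actually treated, for example 8 of 20 (type I error 3.2%) or 9 of 24 (3.6%), and restate power.

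No new visits or measurements are needed. The cost is a lower reported response rate and lower power: with 24 treated, 97% without dropout, 87% at 15% dropout and about 72–75% at 25%. The last is below the stated 80%, so the plan must either declare the lower figure or treat more participants.

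Separately, the rescue limits in 7.4.6.5 (drug stopped after more than three interventions) and in the risk table of 10.0 (up to two) differ and must be reconciled, since the non-responder rule refers to excess rescue.

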7.2 Study Procedures**7.2.1 Screening visit**

Informed consent	Laboratory screening obtained* 
 • Hepatitis B and Hepatitis C surface and core antibodies • Interferon-releasing assay for tuberculosis (or chest x-ray for those with a history of positive PPD) • Complete blood count (CBC) with differential • Hepatic panel (AST, ALT, Alk phos) • Fasting lipid panel (total, high-density, and low density cholesterol and triglycerides) • Pregnancy testing for women of child bearing potential (WOCBP)**
Inclusion/exclusion criteria reviewed	
Complete physical exam	
Clinician assessments (Lesion count, Hurley stage, HASI)	
Clinical photography of all lesions (do not include face)- kept in research files	
ECG	
Alcohol intake and recreational drug use	
Begin weekly surveys (more details below)	

*All blood will be obtained at Penn State Health outpatient laboratory.

**If subjects are postmenopausal, (defined as amenorrhea at least 12 months before screening) this will be confirmed by FSH levels drawn at the clinical site (approx. 2 teaspoons of blood)

Begin weekly surveys – These will be completed by the participants weekly through the end of Week 16 through REDCap. The weekly instruments will include patient-reported measures: NRS pain with 24-hour recall, NRS pain with 7-day recall, Hidradenitis suppurativa Quality of Life instrument (HiSQOL); medication use (assessing use of rescue medications or other potentially modifying medications or interventions).

7.2.2 Week 0, Baseline visit (28 ±5 days)- Can be combined with Screening Visit

Subjects will have a combined Screening/Baseline visit if all Inclusion/Exclusion criteria is met at the Screening visit.

Complete physical exam	Patient reported measures- collected electronically
------------------------	---

Clinician reported measures collected	WOCBP only- urine sample for pregnancy
Clinical photography	Dispense and start treatment with topical ruxolitinib 1.5% cream. Study coordinator will provide instructions for twice daily application.
Target lesion evaluated	Tissue sample collected (details below)

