7.3 Duration of Participation

During the study, participants will have scheduled visits in the Dermatology Research Office at Screening, Baseline/Week 0 (can be combined with Screening), Week 4, Week 8, and Week 16. Each of these visits is expected to last for up to 60 minutes.

Participation will be up to 24 weeks long, including the screening and follow up periods.

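### Section 8.3 pairs a completers-only analysis set with last-observation-carried-forward; on either reading the Week 16 change in the continuous secondary endpoints is at risk of bias, and repeated measures already collected go unused

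*Combined protocol and SAP*

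**What the plan says.** Section 8.3 (Statistical methods) sets the population: "The primary efficacy analysis will be carried out in the ITT Population, defined as all patients who complete the study". Section 1.2 likewise limits the primary analysis to participants who finish 16 weeks of treatment. The next sentence of Section 8.3 is the only missing-data rule in the plan: "Last-observation-carried-forward will be used for missing data". No sensitivity analysis accompanies it.

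For the secondary endpoints, Section 8.3 says: "Secondary efficacy variables will be summarized in the ITT Population". It names no model, test or interval for them. The longitudinal methods it does mention ("Analyses can include paired t-tests, repeated measure ANOVA and regression-based analyses") belong to a passage on laboratory assays.

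Section 7.3 puts clinic visits at "Baseline/Week 0 (can be combined with Screening), Week 4, Week 8, and Week 16", so there is no Week 12 visit. Section 7.2.1 collects HiSQOL and both pain NRS scores by survey: "These will be completed by the participants weekly through the end of Week 16 through REDCap". For participants who withdraw, Section 3.3.2 says: "All attempts will be made to conduct the last study visit and perform all early termination assessments". Section 7.2.5 accordingly combines the Week 16 visit with an early-termination visit that includes clinician and patient measures.

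**The concern.** A completers-only set and a carry-forward rule work against each other. Carry-forward exists mainly to keep leavers in the analysis, and the population definition has already removed them. An analyst could follow either sentence and report a different Week 16 mean change.

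Neither reading is satisfactory. Excluding leavers discards the Week 4 and Week 8 data they provided. It also leaves the result open to selection, since Section 3.3.1 lists worsening HS and unacceptable side effects among the reasons for leaving. Carrying forward labels an earlier state as the Week 16 state and counts it as an observed value. There is no control arm in which a similar error might offset this, so any bias passes straight into the reported change. With 18 to 24 participants, a few such values can matter.

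**Working it through.** The plan gives no SD, correlation, dropout pattern or numerical result for this point, so there is no stated figure to reproduce. The check has four parts.

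**1. Age of a carried value (Sections 7.2 and 7.3).** Carry = 16 minus the week of the last value.
- Clinician measures (HASI, lesion-derived IHS4, AN count): 16 - 8 = 8 weeks; 16 - 4 = 12 weeks; 16 - 0 = 16 weeks if only Baseline exists. An early-termination visit shortens these where it takes place.
- HiSQOL and pain NRS: if the last survey is Week 15, 16 - 15 = 1 week; longer if surveys stopped sooner.

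**2. Amount of dropout.** Section 8.1 plans about 24 people for at least 18 completers: 1 - 18/24 = 25%. That allowance includes screen failures, so 25% is an upper figure for planned loss among treated participants. I use 10% and 25%.

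**3. Leavers excluded.** If a fraction f leaves and leavers' true Week 16 change is worse than completers' by d, the completer mean overstates the all-treated benefit by f × d. With assumed d = 0.5 SD, this is 0.10 × 0.5 = 0.05 SD or 0.25 × 0.5 = 0.125 SD. With d = 0 it is zero. The documents do not give d.

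**4. Leavers carried forward.** Illustrative simulation: 4,000 runs per scenario, N = 24, Weeks 0, 4, 8 and 16, SD 1, correlation 0.6, dropout after Week 4 or Week 8, either completely at random (MCAR) or at random given the data (MAR). All of these inputs are assumptions. True Week 16 change is -1 SD, except -0.6 SD for late loss. Each cell is bias in SD units (coverage of the 95% interval); positive bias means benefit understated.

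| Mean profile | 10% MCAR | 10% MAR | 25% MCAR | 25% MAR |
|---|---|---|---|---|
| Steady improvement | 0.060 (0.942) | 0.085 (0.927) | 0.149 (0.885) | 0.198 (0.849) |
| Early plateau, 80% of effect by Week 4 | 0.010 (0.945) | 0.031 (0.946) | 0.023 (0.944) | 0.077 (0.926) |
| Late loss of effect | -0.030 (0.949) | -0.007 (0.949) | -0.070 (0.932) | -0.018 (0.943) |
| Flat after Week 4 | 0.001 (0.948) | 0.026 (0.950) | 0.001 (0.953) | 0.050 (0.942) |

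Hand check of the first row: if improvement is linear in weeks, a Week 4 value falls 1 - 4/16 = 0.75 SD short and a Week 8 value 1 - 8/16 = 0.50 SD short. With leavers split evenly the average is 0.625 SD. Then 0.25 × 0.625 = 0.156 and 0.10 × 0.625 = 0.0625, close to the simulated 0.149 and 0.060.

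The likelihood-based repeated-measures estimate was biased by at most 0.006 SD in any scenario. At 25% dropout the LOCF interval was 0.74 to 0.80 SD wide, against about 0.87 for completers, so 8% to 14% narrower.

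One limit must be read with the table. The completer estimate was also biased by no more than 0.006 SD. That follows from the assumptions: with one common correlation, the slope of (Week 16 minus Baseline) on an intermediate score is 0.6 - 0.6 = 0, so selection on that score does not shift the mean change. The simulation therefore does not size completer selection; part 3 does so only conditionally on d.

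**The case against.** The strongest reply is that LOCF would hardly operate. If the set is completers, a value is missing only when a completer skips an assessment. This stands, and it means the table describes the second reading, not the plan's literal text. It does not rescue the plan, because the literal text discards leavers' data and makes the LOCF sentence nearly idle.

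Other parts of the reply also stand:
- The LOCF sentence follows the primary-analysis sentence. Its extension to secondary endpoints is an inference. IHS4 and pain NRS are not in Section 8.3's secondary list at all; they appear in Section 1.3.
- A reader might infer that every secondary endpoint has Week 4 or Week 8 values carried to Week 16. The documents do not support that: HiSQOL and pain NRS are weekly, and early-termination visits are attempted for leavers.
- A reader might infer that the plan will report intervals that are too narrow. No interval is planned for these endpoints. In the simulation, undercoverage went mainly with bias, and coverage was nominal for the flat profile under MCAR.
- A simulation with about 35% missing at Week 16 gives bias of 0.06 to 0.25 SD and coverage down to 0.77. Section 8.1 implies at most 25%, so those figures are not a fair guide.
- The near-zero bias of the likelihood estimate is built in, because the simulated dropout was at random. Section 3.3.1's withdrawal for worsening HS may break that assumption, so a sensitivity analysis is needed.

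**Conclusion.** The concern holds as a conflict between two sentences of Section 8.3 plus unused longitudinal data, not as proof that the results will be biased. If leavers are excluded, the risk is completer selection, of size f × d with d unknown. If leavers are carried forward, LOCF bias ran from about -0.07 to +0.20 SD with coverage of 0.85 to 0.95 at 10% to 25% dropout, under assumed SD, correlation and dropout pattern. Bias can go either way: benefit is understated under steady improvement and overstated when the effect is lost late. A reader might go further and infer that bias is certain, or that completer selection has been shown to be the larger error; neither the documents nor the calculations establish that. These are descriptive secondary endpoints in a small single-arm study, so this is a cheap improvement and not a threat to the trial.

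**What to change.** In Section 8.3:
- Define the efficacy set as all enrolled participants who received study drug, and stop using ITT for completers.
- For the continuous secondary endpoints, replace LOCF with a mixed model for repeated measures at Weeks 4, 8 and 16: visit as a factor, baseline score as covariate, unstructured covariance, Kenward-Roger degrees of freedom. Report the Week 16 estimate with its 95% CI.
- Name a simpler covariance structure as fallback. Three visits need 3 × 4/2 = 6 covariance parameters, which is workable. Sixteen weekly surveys would need 16 × 17/2 = 136, which cannot be fitted with 18 to 24 people.
- For HiSQOL and pain NRS, use the survey values at Weeks 4, 8 and 16. Averaging over four weeks would change the Week 16 endpoint in Section 1.3.
- State which visit an early-termination value is assigned to, so that it is not labelled Week 16 by default.
- Add one sensitivity analysis for missing-not-at-random dropout, for example imputation with a stated worsening for leavers. It should include treated participants with no post-baseline score, who contribute nothing to the model above.
- Report the completer summary as supportive.

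The cost is SAP wording and modest programming, with no new visits or participants. Intervals will be somewhat wider than under LOCF.
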